#### 7.2.4 Subgroup analyses

Subgroup analyses for the primary endpoint and secondary outcomes will be performed to determine whether the intervention differs qualitatively across various baseline-defined subgroups. The following baseline characteristics define those subgroups:

Age treated as categorical with levels 17-20, 21-40 and greater than 40.  
Sex.

Subgroup analyses for the primary endpoint will use linear models as used for the primary analysis. Subgroup analyses for the secondary outcomes related to efficacy will use linear models for the first two outcomes (i.e., change in haemoglobin over 4 months and ferritin levels at 4 months), and use logistic regression models for the other three outcomes (i.e., diagnosis of ID or IDA at 4 months, attempt to return for donation within 6 months, and successful donation within 6 months). The explanatory variables will be the subgroup factor and its interaction with the group membership indicator. The null hypothesis that the regression coefficient associated with the interaction is zero will be tested at a significance level of 0.05.

Subgroup analyses will be interpreted with caution since no adjustments for multiple hypothesis testing are planned.

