Questionnaires developed to investigate responses to questions around feasibility and acceptability will serve as response variables in logistic (for binary responses) or proportional odds (for Likert scale type responses) regression models with group membership, sex, and age as covariates. There will likely be many such items and no attempt to control for multiple hypothesis testing will be conducted. As such, the results will be interpreted with caution. Additional analyses will include longitudinal models for ID, IDA, haemoglobin levels and ferritin levels. These models will use generalized estimating equations to account for the repeat measurements from subjects. Conventional significance levels will be utilized for model interpretation. Comparison of the results from the copper sulphate test and haemoglobin levels from the FBC will be examined with logistic regression models. These models will model the probability of the copper sulphate test being positive as a function of haemoglobin levels. Models will be fit separately for men and women. Exploratory analyses will investigate if age or factors relating to diet impact the nature of this relationship.

Subgroup analyses for the primary endpoint and major secondary outcomes, will be performed to determine whether the intervention differs qualitatively across various baseline-defined subgroups. Subgroup analyses will be performed by age and gender. These analyses will be performed by modelling an interaction between the subgroup factor and group membership and testing the null hypothesis that the regression coefficient associated with the interaction is zero.

If necessary, missing data will be handled by multiple imputation via chained equations (MICE), as implemented in SAS PROC MI procedure²⁸.

All statistical analyses will be completed using SAS or R by the University of Minnesota (UMN) DCC

Data Monitoring Guidelines for an Independent DSMB

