**Table 2: Precision of prevalence estimates for ID and IDA.**

Prevalence	Error Margin	95% Confidence Interval
0.2	0.046	0.15, 0.25
0.3	0.053	0.25, 0.35
0.4	0.056	0.34, 0.46
0.5	0.057	0.44, 0.56

**Parallel groups study:** The primary outcome for this portion of the study is haemoglobin levels at 4 months. Formally the null hypothesis for this outcome is inferiority of treatment of low haemoglobin with iron supplementation among those with

low haemoglobin at screening to no treatment among those without low haemoglobin at screening. The non-inferiority margin is fixed at a value of 1.0 g/dL. Based on recent work in West Africa, the DCC has access to haemoglobin measurements from 1548 individuals between the ages of 17 and 60 who weigh at least 50 kg. Among these individuals the standard deviation of haemoglobin was 1.89 g/dL (the mean was 13.4 g/dL). These individuals did not pass the strict screening criteria used by the NBSG, so this estimate might be slightly inflated and so our power calculations may be somewhat conservative. We specify an alpha level of 0.025 and require power of at least 85%. With these values we can determine the number of participants per arm if we assume a value for the true difference between the groups (the absolute value of this difference must be less than our margin and will generally be negative when the margin is positive to be consistent with the lack of superiority of iron supplementation). Table 3 presents the number of participants per arm under these assumptions for a selection of values for the true difference. We assume that the true difference is -0.3 g/dL and obtain a sample size of 131 participants per arm. If the true difference is larger than -0.3 g/dL (e.g., if there is no difference) then the power will exceed 85%. To allow for loss to follow-up and some participants requiring iron supplementation due to incident anaemia, ID or IDA the sample size has been increased to 292.

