## 2.5 Framework and statistical principles

The qualitative study that precedes the trial will be used to guide implementation and evaluation of the larger study at the UH3 Phase, including identifying barriers and recommendations for using iron supplementation and nutritional counselling to increase the blood donor pool. Moreover, qualitative findings resulting from focus groups to be conducted at the end of the trial and key informant interviews will be used to guide the planning, implementation, and evaluation of the UH3 phase.

The following general principles will apply to this pilot. All confidence intervals (CIs) are 2-sided and at the 95% level and hypothesis tests are 2-sided at the 5% significance level unless otherwise specified. Percentages, means, medians and quartiles will be rounded to one significant digit. P-values will be given to 2 significant figures. Version

9.3 (or later) of SAS and/or version 3.5 (or later) of R will be used to conduct the analysis and generate tables and figures.

Descriptive statistics for enrolment rates over time and the proportion of participants completing the 6-month study visit will be assessed by treatment group. Those statistics will be used to determine the feasibility of the larger study (UH3) and may lead to changes in how consent, enrolment, and follow-up are conducted.

**Cut-date for interim reviews:** Analysis data sets will be frozen (locked) several days (or weeks) prior to the review date, to allow the statisticians time to prepare a consistent report. The cut-date may be earlier than the date of the data freeze, to allow for additional time for the reporting of events.

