#### Primary analysis

The analysis for the primary outcome of haemoglobin levels at 4 months will be conducted using a linear model with haemoglobin levels at 4 months as the response variable. It is unlikely that there is a need to transform the response variable as haemoglobin levels are usually symmetrically distributed with tails that decay at rates consistent with the normal distribution. However, if informal univariate assessments of normality (e.g., qq-plots) indicate strong departures from these expectations, the Box-Cox transformation will be used to select a transformation. The set of explanatory variables will be group membership (i.e., received iron supplementation at enrolment or not), screening haemoglobin, sex, and age. A 1-sided t-test for the regression coefficient associated with group membership will be conducted with a significance level of 0.025 to test the inferiority hypothesis. This analysis will exclude individuals who did not receive iron supplementation at enrolment but received it during follow-up due to changes in ferritin or haemoglobin values. The frequency of this will be closely tracked and if more than 10% of participants in the group initially not receiving iron supplementation receive iron supplementation during follow-up, alternative analysis approaches will be considered and presented to the DSMB.

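### As listed, the subgroup models omit the group main effect, so their interaction test checks for a group effect within subgroups rather than for a difference in effect between them

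*SAP*

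**What the plan says.** SAP 7.2.4 plans subgroup analyses by sex and by age for the primary endpoint and the secondary outcomes. Age has three levels: "Age treated as categorical with levels 17-20, 21-40 and greater than 40". The models are described as follows.

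- Primary endpoint: "Subgroup analyses for the primary endpoint will use linear models as used for the primary analysis". That primary model is given in 7.2.1: "The set of explanatory variables will be group membership (i.e., received iron supplementation at enrolment or not), screening haemoglobin, sex, and age".
- Five secondary efficacy outcomes: linear models for two and logistic models for three, with no reference back to the models of 7.2.2.
- Terms: "The explanatory variables will be the subgroup factor and its interaction with the group membership indicator".
- Test: "The null hypothesis that the regression coefficient associated with the interaction is zero will be tested at a significance level of 0.05". SAP 2.5 makes it two-sided by default: "hypothesis tests are 2-sided at the 5% significance level unless otherwise specified".

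The protocol (Data Analysis, Quantitative Data Analysis) speaks of "modelling an interaction between the subgroup factor and group membership" and of testing that its coefficient is zero. It does not list the remaining terms.

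**The concern.** The stated purpose of 7.2.4 is to learn whether the intervention's effect differs across subgroups. An interaction coefficient measures such a difference only when the model also contains the group main effect. Without it, the coefficient attached to subgroup-by-group is simply the group effect within a level of the subgroup factor.

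A group difference that is identical in men and women could then be reported as a difference by sex. This matters because a zero group difference is not the expected state. The sample size assumes -0.3 g/dL. The arms are also formed by low haemoglobin or iron deficiency, so they are likely to differ on change in haemoglobin, ferritin and ID/IDA status. A false subgroup signal could carry into the planning of the UH3 phase.

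**Working it through.** **1. The plan's own figure.** SAP 2.4 supplies the SD ("Among these individuals the standard deviation of haemoglobin was 1.89 g/dL"), margin 1.0, assumed difference -0.3, one-sided alpha 0.025 and power 85%.

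n per arm = 2 × SD² × (z₀.₉₇₅ + z₀.₈₅)² / (margin − shortfall)² = 2 × 1.89² × (1.960 + 1.036)² / 0.7² = 130.9, rounded up to 131.

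The same formula returns 65, 80, 101 and 179 for the other rows of Table 3. Allowing 10% loss, 262 / 0.9 = 291.1, which becomes 292 with equal arms. The design inputs therefore reproduce and are used below.

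**2. What the listed terms estimate.** Let S = 1 for men and 0 for women, and G = 1 for iron.

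- Listed terms, single product column: E(Y) = a + bS + c(S×G). Here c is the group effect in men, and the effect in women is fixed at zero.
- Listed terms, one product per level: E(Y) = a + bS + c₀((1−S)×G) + c₁(S×G). Here c₀ and c₁ are the group effects in women and in men.
- With the main effect: E(Y) = a + bS + dG + e(S×G). Here e is the difference between the two effects.

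Only the last form tests heterogeneity. In the first, the answer also depends on which level is the reference.

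**3. Closed-form rejection rate, product-column coding.** For a level holding share p of each arm, SE = 1.89 × √(2 / (131p)). The rate at common effect δ is Φ(−1.96 + |δ|/SE) + Φ(−1.96 − |δ|/SE). The documents say only that well over half of donors are men, so 50–70% men is an assumption.

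| Tested level's share | SE | δ = 0 | δ = -0.3 | δ = -0.5 | δ = -1.0 |
|---|---|---|---|---|---|
| 30% (women tested) | 0.426 | 5.0% | 10.8% | 21.6% | 65.0% |
| 50% | 0.330 | 5.0% | 14.9% | 32.8% | 85.7% |
| 70% (men tested) | 0.279 | 5.0% | 18.9% | 43.3% | 94.8% |

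**4. Simulation.** 10,000 data sets per setting, n = 262, 1:1 allocation, SD 1.89, the same effect in every subgroup, two-sided 5% test, and no covariates beyond the subgroup factor. Age shares of 25/60/15 and 10/70/20 are assumed.

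| Common effect (g/dL) | Sex, product column | Age, product columns | Sex or age, all level-specific terms jointly | Main effect included |
|---|---|---|---|---|
| 0 | 4.7–4.8% | 5.0–5.2% | 4.8–5.3% | 4.9–5.3% |
| -0.3 | 10.6–18.9% | 15.1–17.4% | 16.2–18.5% | 4.9–5.3% |
| -0.5 | 20.6–42.7% | 35.4–41.8% | 38.7–45.7% | 4.9–5.3% |
| -1.0 | 62.0–94.6% | 91.8–96.1% | 96.0–97.6% | 4.9–5.3% |

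The simulated rate falls slightly below the closed form at -1.0 because the unmodelled effect in the reference level adds to the residual variance. With 70% men as reference, it becomes 1.89² + 0.7 × 1.0²/4 = 3.75, against 3.57.

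If covariates were retained and brought the residual SD to an assumed 1.2, the rates at -0.3 would rise to 19–41%.

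**5. Logistic outcomes.** 1,000 data sets, n = 262, 70% men, women as reference, with assumed control-arm rates of about 40% in women and 48% in men. The two-term model rejects in 4.7% at a common odds ratio of 1, 61% at 0.5 and 99.7% at 0.25. With the main effect included the rates are 4.8%, 5.8% and 4.8%. The odds ratios are illustrative; the documents give none.

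**The case against.** The best defence is that the plan never commits to the bare two-term model. For the primary endpoint, 7.2.4 points back to a model that contains group membership. For the secondary outcomes, 7.2.2 specifies models with group, screening haemoglobin, screening ferritin, sex and age, using the same linear/logistic split that 7.2.4 repeats. The sentence on terms could therefore name only what is added. The protocol describes an ordinary interaction test, and nothing says the main effect is dropped. The singular coefficient in the test sentence also suits the conventional model for sex.

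Much of this stands for the primary endpoint, where the text is ambiguous rather than definitely wrong. It is weaker for the secondary outcomes. The reference to the primary model covers the primary endpoint alone, and 7.2.4 makes no link to 7.2.2. The sentence has the form of a complete list. Where the SAP means that interactions extend an existing model, as in its copper sulphate analysis under Additional Analyses, it says that they are added.

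The defence is also right that fixing the reference level's effect at zero is a feature of one coding only. A formula-based fit would give one group effect per level. The joint test of those effects is still a test for any group effect, and its rejection rate is similar or higher.

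Finally, these are unadjusted subgroup tests in a pilot, to be read with caution. The caution given in 7.2.4 concerns multiplicity, though. It does not cover a coefficient that answers a different question.

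**Conclusion.** The term list in 7.2.4 needs correction. It is the section's only specification for the five secondary efficacy outcomes, and for the primary endpoint it is at odds with, or unclear against, the reference to the primary model. Fitted literally, it gives a nominal 5% test that rejects about 11–19% of the time at a uniform -0.3 g/dL and 62–98% at -1.0 g/dL, depending on coding, reference level and sex mix. These figures rest on n = 262 and SD 1.89 from the SAP, and on the assumed sex and age shares. The SD of change in haemoglobin is not given, so the g/dL rates are only a guide for that outcome.

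A reader might infer that the plan will report a false subgroup difference whenever the iron effect is uniform. The documents do not support that. At a common effect of zero the rate stays near 5%, at the design value most data sets would still not reject, and the -1.0 figures describe an effect at the margin itself. Nor do the documents show that the primary-endpoint subgroup analysis would be run without the group term. The primary non-inferiority test does not use these models and is unaffected.

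**What to change.** Replace the sentence on explanatory variables and the one on the test in SAP 7.2.4 with:

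*Each subgroup model will contain all terms of the corresponding main analysis (7.2.1 or 7.2.2), including group membership, plus the group-by-subgroup interaction. For the age subgroup analysis, three-level categorical age replaces continuous age. The interaction is tested at the two-sided 0.05 level, with 1 df for sex and a joint 2-df test for age.*

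Sex and age are already in the main models, so the subgroup factor should not be entered a second time. That is why categorical age replaces continuous age rather than joining it. The joint test is needed because three age levels give two interaction coefficients, while the present text refers to one.

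The cost is a short SAP edit, which section 1.1 allows until database lock. No change to data collection, sample size or the primary analysis is needed.

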#### 7.2.5 Preventing and accounting for missing data

Missing data will be prevented by several procedures. These start with prioritizing retention through follow-up in the recruitment and consenting procedures, and this will be emphasized during site training and on protocol team calls. During conduct of the trial, visit completion rates and case report form data completeness will be monitored closely. Missing data from the analysis of the primary and secondary endpoints will be handled by multiple imputation via chained equations (MICE), as implemented in SAS PROC MI procedure. This method can handle both binary outcomes and ordinal categorical outcomes. The multiple imputation model will include the demographic characteristics listed in section 3.4. Twenty rounds of imputation will be used.

### 8 Interim Monitoring Guidelines for the DSMB

The DSMB will periodically review and evaluate the accumulated study data for participant safety, study conduct and progress, and, when appropriate, efficacy. Recommendations to continue, terminate, or modify the study will be made by the DSMB, however there are no formal stopping criteria for this small pilot study. Interim data summaries will be prepared by the DCC statisticians and reviewed at regular intervals by the DSMB (at least twice a year). Regulatory requirements and site-level interim monitoring will be tracked by the DCC. Safety data reports will be generated and reviewed by the DSMB at more frequent intervals if the DSMB requests such reports. Additional data summaries may be requested by the DSMB. The DSMB will make

recommendations concerning continuation, modification, or termination of the study after each meeting.

## 9 Data Completeness and Study Conduct

Data completeness and study conduct reports will be provided to DSMB by treatment group (for the closed report) and pooled across treatment groups (for the open report).

The following data summaries will be provided to assess data completeness and study conduct:

Number and percent of participants with deviations from protocol, and type of protocol deviation.

Number and percent of participants who consented and were administratively withdrawn. This will be further summarized by withdrawal due to ineligibility (due to laboratory values or expiration of laboratory values) or not.

Number and percent of participants who withdrew consent or were lost to follow-up (i.e., the participant did not return for the 6-month visit and the window for that visit has closed).

If more than 10% of participants are lost to follow-up, the cumulative proportion of participants who are lost to follow-up over time will be estimated by the Kaplan-Meier method. These estimates will be provided by treatment group (closed report only).

Listing of participant identifiers who initiated withdrawal of consent, the dates of enrolment of those participants, study treatment assignment, date of withdrawal, and reason for withdrawal.

The number of each eCRF that has been completed and the expected values for these numbers.

Length of follow-up summarized by median, IQR, and range.

The number and percentage of participants who have completed follow-up.

## 10 Distribution of Reports

Open report: BLIS leadership team; selected staff from the National Institutes of Health (NIH) and the NHLBI of the United States; and all recipients of the closed report.

Closed report: DSMB members.

The results at the end of the study: NBSG, Ghana Health Service, NIH and NHLBI of the United States, publications in peer-reviewed journals, conference presentations and mass media.

## Appendix A. Schedule of Assessments

Assessment	Screening (Day -14 to 0)	Enrolment (Day 0)	Biweekly (Throughout)	Interim Visit 1 (Week 8-10)	Interim Visit 2 (Week 16-18)	Final Visit (Week 24)
NBSG Pre-Donation Assessment	X					X
Informed Consent	X					
Inclusion and Exclusion Criteria	X					
Demographics	X					
Full Blood Count and peripheral blood comment	X			X	X	X
Plasma Ferritin	X			X	X	X
Malaria Parasites Testing (RDT)	X	X		X	X	X
Nutritional Counselling		X		X	X	
Qualitative Assessment						X
Follow-Up Calls			X			
Return Blood Donation Status				X	X	X
Assessment for Adverse Events		X	X	X	X	X
Adherence Assessment (for those receiving supplemental iron)			X	X	X	X
RDT – Rapid Diagnostic Test						

**Appendix B. List of Acronyms**

AE	Adverse event
BLIS	Bloodsafe Ghana- Iron and Nutritional Counselling Strategy Pilot Study
DCC	Data Coordinating Centre
DSMB	Data and Safety Monitoring Board
eCRF	Electronic Case Report Forms
FBC	Full Blood Count
FGD	Focus group discussion
GEE	Generalized estimating equations
Hb	Haemoglobin
ID	Iron Deficiency
IDA	Iron Deficiency Anaemia
IRB	Institutional Review Board
NBSG	National Blood Service Ghana
NHLBI	National Heart, Lung, and Blood Institute
SAE	Serious adverse event
SAP	Statistical analysis plan
SZBC	Southern Zonal Blood Centre
TTI	Transfusion Transmissible Infection
